6.4.3. Follow-up MSAT

A follow-up MSAT will be triggered if the estimated URDT prevalence of the M12 survey is $\geq 5\%$. It will follow the same procedures as the baseline MSAT.

7. STUDY PROCEDURES

7.1. Recruitment

Villages will be allocated to group 1 (programmatic MSAT) based on incidence over the previous 12 months. This list will be revised twice per year after each transmission season (February and August). Villages will be allocated to group 2 (reactive MSAT) based on weekly analysis of malaria surveillance data (see details in 6.1).

Following the allocation of villages to a given group and the decision to conduct the intervention, the community engagement team will conduct meetings in the village/cluster to explain the purpose of the intervention and seek community approval, first with village and local authorities, then with the entire population. After the agreement from the community, a date will be set for the intervention and the mobilization and engagement of individuals will begin, involving CE team members and the MP worker from the village.

The MSAT intervention will be conducted by visiting participants at home or by inviting them to a central location, depending on the lay-out of the village and the preferences of the populations. Participant information will be discussed individually and participant will be recruited in the MSAT intervention after informed consent. The same procedure will be followed for M12 follow-up survey in Group 1.

7.2. Informed Consent

The MSAT intervention will first be explained to the community, through meetings with leaders and authorities, public meetings with all individuals and meetings and activities for specific groups of participants (school-age children...). Seeking community consent first will allow time for the population invited to participate to discuss with field team members and with each other, to ask questions and address concerns. Participant information will be presented under different forms during these activities.

At inclusion, written and verbal versions of the Participant Information and Informed Consent will be presented to the participants detailing: the exact nature of the study; what it will involve for the participant; the implications and constraints of the protocol; the known side effects and any risks involved in taking part. It will be clearly stated that the participant is free to withdraw from the study at any time for any reason without prejudice to future care, and with no obligation to give the reason for withdrawal.

The participant will be allowed as much time as wished to consider the information, and the opportunity to question the field team or other independent parties to decide whether they will participate in the study. Written Informed Consent will then be obtained by means of participant dated signature and dated signature of the person who presented and obtained the Informed Consent. The person who obtained the

consent must be suitably qualified and experienced, and have been authorised to do so by the Chief Investigator. A copy of the signed Informed Consent will be given to the participant. The original signed form will be retained at the study site.

For children ≥ 10 to < 18 years old, an assent will be obtained in addition to the consent of their parent or guardian. For children below 10 years, the consent of the parent or guardian will be obtained.

A second consent will be collected upon participation to the follow-up survey, 12 months after MSAT intervention.

7.3. Screening and Eligibility Assessment

All participants who consent to be tested and treated if falciparum positive will be eligible to participate in the MSAT intervention.

7.4. Randomisation, blinding and code-breaking

No randomization will be conducted. Villages with sustained high incidence will be assessed every 6 months and prioritized based on accessibility/feasibility. As much as possible, all villages from a given area will be addressed at the same time in order to maximize impact of interventions.

7.5. Baseline Assessments

The baseline assessment (D0) will occur immediately after inclusion. Participants will be asked baseline demographic data (age, sex, visitor status, occupation and activities during the previous month) and baseline clinical data (temperature and history of fever over the previous week), which will be recorded in a logbook where each patient will be identified by a unique number printed on a sticker that will also be used to label the URDT, the sample(s) collected from the participant.

In **group 1 only**, participants will undergo a finger-prick from which capillary blood will be collected using the lancet provided by the URDT manufacturer in order to realize the URDT. From the same finger-prick, 50 μ L of capillary blood will also be collected on an EDTA microtube, labelled with a participant sticker.

The URDT will be read by a trained field worker following the manufacturer's instructions. If the test is positive, a second finger prick will be conducted in order to collect an additional blood sample on filter paper (3x 1cm blood spots), labelled with a participant sticker.

If the test is positive, a physical and clinical examination will be conducted. Female participants of child-bearing age will be asked if they are or could be pregnant and proposed to take a pregnancy test if unsure. History of malaria diagnosis and treatment during the previous week will be collected. The weight of the participant will be measured and history of previous allergies to drugs and specifically antimalarials will be collected. A curative treatment for *P. falciparum* malaria will be administered to falciparum-positive participant following a weight-adjusted dosage and according to each participant characteristics (see 8. intervention).

The willingness and ability of eligible participants to take a complete treatment will be assessed by the fieldworker, and the importance of completing the treatment will be discussed with the participant if

necessary. The first dose of treatment will be administered directly, and recorded in the logbook. An appointment will be set for the next dose on the following day.

Participants who declare being unable to attend supervised treatment for the next takes will be given the remaining doses (expected <2.5% of treatments initiated).

7.6. Subsequent Visits

7.6.1. Treatment administration follow-up visits (visit 2, visit 3)

Subsequent visits will be conducted on the second and third day of standard DP antimalarial treatment for individuals receiving the standard DP course (D1, D2). Before administering the next dose, a small questionnaire will be used to collect potential adverse events or other complaints.

For 1st trimester pregnant women treated with Q/C, the village malaria post worker will be in charge of completing the follow-up of the 7-day treatment course as per his training. For patients receiving other types of treatment, a team medic will follow-up the completion of the treatment and monitor for AE daily.

7.6.2. Malaria incidence monitoring

Each village is equipped with a community-based malaria post, where a trained member of the community provides diagnosis and treatment to all fever cases occurring in the village. The MP records the result of all RDT conducted and reports weekly activity data, including number of fever consultations, number and result of RDT performed and number of clinical malaria episodes treated by sex and age-group of patient and by parasite species.

7.6.3. Follow-up prevalence survey (group 1)

Twelve months after the beginning of the MSAT campaign in group 1 villages (high incidence), a population list will be collected again and a prevalence survey will be conducted in a sample of village inhabitants to perform URDT and collect a sample of 50µL for reference testing (sample size based on ability to measure a 90% decrease from baseline, see 9.2).

After the subsample of inhabitants has been surveyed, if the URDT prevalence is above 5%, the survey will shift to an MSAT round following the same protocol as baseline. If the URDT prevalence is below 5%, the positive individuals will be referred to MP for treatment and the survey will finish.

This survey will identify households from the MSAT campaign, but not match individual identification codes.

Since the procedures and interventions are similar to

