4. OBJECTIVES AND OUTCOME MEASURES

Objectives	Outcome Measures	Timepoint(s) of evaluation of this outcome measure (if applicable)
Primary Objective To measure the impact of URDT-based MSAT on P. falciparum incidence at village-level.	Adjusted incidence rate ratio before/after MSAT	Follow-up from MP opening to end of study
Secondary Objectives 1) To measure the impact of MSAT on prevalence of P. falciparum infection in malaria hotspots	1) Prevalence of P. falciparum infection measured in the village by URDT and by reference method (group 1)	1) Comparison between M0 survey (during MSAT) and M12 survey (12 months after)
2) To measure the impact of reactive MSAT on incidence of seasonal malaria peaks / outbreaks.	2) Change in the incidence dynamics over the transmission season (group 2)	2) Duration and height of seasonal peak before, during and after reactive intervention
3) Feasibility of MSAT as a programmatic tool and as a reactive strategy.	3) Coverage of village population with intervention	3) coverage based on census conducted before/during MSAT
4) % of infections treated compared to infections detected by reference method	4) % of P. falciparum positive samples by reference method which were positive by URDT and treated; % of P. falciparum negative samples by reference method which were positive by URDT and treated (group 1)	Group 1 only
Tertiary Objectives Retrospective comparison of MSAT versus MDA on prevalence and incidence of P. falciparum malaria	Cumulative incidence of falciparum malaria episodes before and after MDA/MSAT; prevalence of falciparum infection before and after MDA/MSAT	Entire incidence series

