7.8. Discontinuation/Withdrawal of Participants from Study

The follow-up and study outcomes are defined at the village-level and apply to village populations rather than individuals. An eligible village will be excluded from the study if:

- the MSAT intervention can't be conducted (refused by the community, impossible to access)
- the population size changes by $\geq 50\%$ between MSAT and follow-up survey.

Each participant has the right to withdraw from the study at any time.

In this study, systematic individual follow-up will occur during the MSAT intervention period and after the MSAT intervention to monitor demographics and clinical case incidence.

During the MSAT intervention individual follow-up will be conducted to ensure that a complete treatment is taken by all individuals found infected with *P. falciparum*. In the light of the threats of artemisinin-resistance, it will however be necessary to ensure that all falciparum-positive individuals are treated and that all individuals initiating a treatment take a complete curative course. Counselling will be provided to participants wishing to discontinue their participation. The counsellors will be members of the CE team with an extensive experience of interventions requiring the treatment of asymptomatic participants (filariasis and/or malaria mass drug administration campaigns in the region). In case the participant refuses to continue his/her antimalarial treatment course outside of the study, he/she will be offered to receive standard treatment for falciparum clinical malaria (AL+sld PMQ) from the village MP, or referred to the nearest health facility. The reason for withdrawal will be recorded in the MSAT logbook.

Individuals or households moving in or out of the village will be assessed during the M12 follow-up. Newcomers will contribute to the village follow-up and be included in the prevalence survey if they match inclusion criteria.

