9. STATISTICS AND ANALYSIS

9.1. Description of Statistical Methods

Coverage of intervention: the coverage of the intervention will be defined as the proportion of individuals screened by URDT divided by the total number of individuals present in the village during the next

Before/after MSAT yearly cumulative incidence and 95% Poisson confidence intervals will be calculated using:

- Numerator: the total number of *P. falciparum* cases reported during the weeks with an MP report.
- Denominator: the village population size measured during the MSAT * number of weeks with an MP report during the year (number of weeks of MP activity).

Analysis including the entire follow-up available for malaria posts will be conducted in order to provide adjusted estimates on the

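### Carriers found by study screening can be sent to the village malaria post, whose case count is the primary endpoint, and no rule marks them or keeps them out of the post-MSAT numerator

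*Combined protocol and SAP*

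**What the plan says.** Section 7.6.3 times the M12 survey from the start of the campaign: "Twelve months after the beginning of the MSAT campaign in group 1 villages". What then happens to positives depends on the village result. Above 5% URDT prevalence, "the survey will shift to an MSAT round following the same protocol as baseline". Otherwise, "If the URDT prevalence is below 5%, the positive individuals will be referred to MP for treatment and the survey will finish". Section 7.8 gives a second route in any MSAT village: a person who will not continue study treatment is "offered to receive standard treatment for falciparum clinical malaria (AL+sld PMQ) from the village MP".

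The MP supplies the endpoint data. Section 7.6.2 describes a worker who "provides diagnosis and treatment to all fever cases occurring in the village", and adds: "The MP records the result of all RDT conducted and reports weekly activity data". That weekly report lists RDT results and clinical episodes treated as separate items. The section 9.1 numerator is the total of P. falciparum "cases reported during the weeks with an MP report".

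Three time windows are given. Section 9.3 uses 12 months either side of MSAT. Section 4 uses "Follow-up from MP opening to end of study". Section 9.1 adds an analysis of all available MP follow-up. Section 7.9 ends the study at 12 months if URDT prevalence is under 5% and its upper confidence limit is under 10%.

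**The concern.** The endpoint is meant to be clinical falciparum episodes found passively, when people with fever come to the MP. The two routes above send that MP people who were found actively, many of them without symptoms. If the MP logs them as P. falciparum cases, the after-MSAT count mixes survey prevalence with clinical incidence. The before-MSAT count has no such source, because no study screening took place then.

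At stake is a rate ratio pulled toward 1. The pull is proportionally largest where few clinical cases remain. It could not be undone later from the planned data: section 7.6.2 describes weekly aggregates, section 5 plans no individual link between infection status and clinical episodes, and section 7.6.3 does not match individual codes. Section 10.2 does list individual clinical case data among the study records, but nothing says that they would identify a referral.

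**Working it through.** **1. Survey size (the plan's own figure).** Section 9.2.2.1 gives 60 to 120 samples per village. Inputs: 16% average prevalence (9.2.2.2) and a 90% fall, so p = 1.6%. This is under 2%, so the interval width is 200% of p and the half-width is h = 1.6 points.

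- n0 = 1.96² × p(1 − p)/h² = 3.8416 × 0.016 × 0.984/0.016² = 236.
- With finite population correction, n = n0/(1 + (n0 − 1)/N). For N = 80, 190 and 240 this gives 60, 106 and 119.

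The stated range is reproduced; N = 80 and N = 240 are assumed village sizes.

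**2. Referrals possible per village.** The largest whole number strictly below 5% is 2 of 60 (3.3%) and 5 of 120 (4.2%). If true URDT prevalence is 1% to 4% (assumed), the binomial mean given a result below 5% is 0.5 to 1.3 at n = 60 and 1.2 to 3.5 at n = 120.

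**3. Do they fall in the window?**

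- *Section 9.3 (12 months).* The survey is at Day 365 from campaign start (7.6.3, Appendix B), and a campaign lasts about one week (section 3). If the after year runs from campaign start, it closes as the survey opens and overlap is essentially nil. If it runs from campaign end, it closes at about Day 372, so about one week is inside. The plan does not say which applies.
- *Section 9.1 (all MP follow-up).* Inside.
- *Section 4 (to end of study).* This depends on the 7.9 rule. Exact 95% upper limits for results below 5%:

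| Positives/sampled | Upper limit | 7.9 end rule met? |
|---|---|---|
| 1/60 | 8.9% | yes |
| 2/60 | 11.5% | no |
| 3/80 | 10.6% | no |
| 2/106 | 6.7% | yes |
| 4/106 | 9.4% | yes |
| 5/106 | 10.7% | no |
| 5/120 | 9.5% | yes |

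Referrals fall inside the section 4 window only in the villages marked no.

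- *Section 7.8 route.* These people would reach the MP within days of MSAT, near the start of the after period. The plan gives no expected number.

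**4. Size if counted.** Inputs: 190 inhabitants and 250/1000/year (9.2.1); 125 to 20/1000/year after MDA (9.2.3), as a very good result; a halving from 250 to 125 (assumed). Cases = 190 × rate/1000. Assume that every referral attends, is recorded and falls in the window.

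| Scenario (/1000/year) | Cases before, after | Ratio | +2 referrals | +5 referrals |
|---|---|---|---|---|
| 250 to 125 | 47.5, 23.75 | 0.50 | 25.75/47.5 = 0.54 | 28.75/47.5 = 0.61 |
| 125 to 20 | 23.75, 3.8 | 0.16 | 5.8/23.75 = 0.24 | 8.8/23.75 = 0.37 |

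Each person arriving by the 7.8 route and recorded adds 1/47.5 = 0.02 or 1/23.75 = 0.04 to that village's ratio.

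**5. Pooled.** If half the villages are affected (assumed) with 2 referrals each, the mean addition is 1 case per village: 24.75/47.5 = 0.52 (from 0.50), and 4.8/23.75 = 0.20 (from 0.16).

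**6. If the MP retests by standard RDT (assumed).** In Appendix D, field RDT detected 43 uPCR-positive samples and field uRDT 80; 43/80 = 0.54. The shifts roughly halve: 24.25/47.5 = 0.51 and 4.3/23.75 = 0.18. If the window closes before the survey, the M12 shift is zero.

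**The case against.** **The primary window nearly excludes M12 referrals.** This largely stands. Referral follows a new population list and a completed subsample, so even when time runs from campaign end, the overlap is at most about a week. What remains is that the boundary is undefined and that the entire-follow-up analysis includes the referrals.

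**Most villages below 5% end the study at M12.** This stands for results such as 2/106. A reader might infer that the section 4 window always includes the referrals; section 7.9 does not support that. It includes them only where the upper limit is 10% or more.

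**An afebrile referral is not a clinical episode.** Section 7.6.2 describes the MP as serving fever cases and lists clinical episodes separately from RDT results, so entry into the numerator is possible but not established. Still, section 9.1 counts cases the MP reports, and the plan does not say how such a person is logged. Sections 7.6.3 and 9.1 both break off mid-sentence in the text available, so a rule could have been lost there.

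**The bias singles out villages where MSAT worked.** A reader might infer this from the 5% rule. The documents do not support it. Below 5% is a level, not a fall, so a village that began low qualifies without any effect. The 7.8 route applies in any MSAT village. Group 2 has no M12 survey, although the primary outcome covers both groups.

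**The bias cannot create a benefit.** Correct: it runs against MSAT.

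**Conclusion.** The point holds as a gap in counting rules. The plan can add actively found carriers to the post-MSAT case count, has no matching source before MSAT, and contains no readable rule to mark or remove them. It does not show that the 12-month primary estimate will be biased: M12 referrals enter that window for no more than about a week, and only if the MP records them as cases. The clearer exposures are the entire-follow-up analysis, villages below 5% that do not meet the 7.9 end rule, and people who leave study treatment early in the after period.

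The per-village shifts (0.50 to 0.54, 0.16 to 0.24) are upper cases for 2 referrals, all assumed recorded and in the window. The pooled shifts (0.50 to 0.52, 0.16 to 0.20) also assume that half the villages are affected. All are toward no effect, roughly halve under RDT retesting, and vanish for M12 referrals if the window closes first. The change is worth making because it is cheap and unmarked weekly totals cannot be separated afterwards.

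**What to change.** 1. In 7.6.3 and 7.8, have the MP mark study-referred patients in its log and report them separately in its weekly return.
2. In 9.1 and 9.3, exclude marked patients from the clinical case numerator in every analysis, including the entire-follow-up one.
3. In 9.3, state whether the after period runs from the start or the end of the campaign. End each group 1 village's 12-month after window with the last complete reporting week before its M12 survey begins, and drop the matching calendar week or weeks from the before window. Whole weeks fit the weekly data.

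This changes how these people are counted; their treatment is unchanged. The cost is one mark in the MP log, a few sentences in the plan, and 1 to 2 of 52 weeks per window. The marking has to be in place before the first MSAT round, because the 7.8 route opens then.

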7.7. Sample Handling

From the same finger-prick used to perform the URDT, 50µL of capillary blood will also be collected on an EDTA microtube, labelled with a participant sticker and transported to SMRU laboratories or stored immediately at -80°C in a dry-shipper liquid-nitrogen tank before transport. Upon reception at SMRU laboratories, the samples will be and stored at -80° C until processed for reference malaria detection by Quansys ELISA.

If the test is positive, a second finger prick will be conducted in order to collect an additional blood sample on filter paper (3x 1cm blood spots), labelled with a participant sticker, dried and stored in a plastic blister with silica gel. The DBS will be sent to MORU laboratory in Bangkok for DNA extraction and analysis by GENRE Mekong ([name], Mahidol Oxford Research Unit & Sanger Institute, UK) or MIVS-ACT ([name], Faculty of Tropical Medicine, Mahidol University, Thailand and Mahidol Oxford Research Unit) projects.

The follow-up survey 12 months after MSAT will follow the same procedures. The samples will be transported to SMRU laboratories and stored at -80°C until processed for reference malaria detection by Quansys ELISA.

7.8. Discontinuation/Withdrawal of Participants from Study

The follow-up and study outcomes are defined at the village-level and apply to village populations rather than individuals. An eligible village will be excluded from the study if:

- the MSAT intervention can't be conducted (refused by the community, impossible to access)
- the population size changes by $\geq 50\%$ between MSAT and follow-up survey.

Each participant has the right to withdraw from the study at any time.

In this study, systematic individual follow-up will occur during the MSAT intervention period and after the MSAT intervention to monitor demographics and clinical case incidence.

During the MSAT intervention individual follow-up will be conducted to ensure that a complete treatment is taken by all individuals found infected with *P. falciparum*. In the light of the threats of artemisinin-resistance, it will however be necessary to ensure that all falciparum-positive individuals are treated and that all individuals initiating a treatment take a complete curative course. Counselling will be provided to participants wishing to discontinue their participation. The counsellors will be members of the CE team with an extensive experience of interventions requiring the treatment of asymptomatic participants (filariasis and/or malaria mass drug administration campaigns in the region). In case the participant refuses to continue his/her antimalarial treatment course outside of the study, he/she will be offered to receive standard treatment for falciparum clinical malaria (AL+sld PMQ) from the village MP, or referred to the nearest health facility. The reason for withdrawal will be recorded in the MSAT logbook.

Individuals or households moving in or out of the village will be assessed during the M12 follow-up. Newcomers will contribute to the village follow-up and be included in the prevalence survey if they match inclusion criteria.

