6.2. Study Participants

Since the study will be performed at cluster/village level, the population of study villages will be included and monitored as a whole for the primary outcome on falciparum malaria incidence in the village. Likewise, change in prevalence will be measured by a follow-up survey at village level without matching individuals from MSAT screening to follow-up survey.

MSAT intervention and follow-up surveys will be conducted on individual participants. All population of the cluster/village will be eligible for participation in the MSAT campaign. For the follow-up survey, only residents living in the village for >1 months will be considered in order to assess the reservoir in the village population and limit the contribution of imported carriage.

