6.3. MSAT intervention

6.3.1. Inclusion criteria

All persons living in the village or cluster of villages will be eligible for MSAT intervention. Individuals living in smaller settlements (permanent or temporary) within walking distance of a selected intervention village will also be eligible.

Large “work-related” settlements in the vicinity of a targeted village (military camps, logging camp, mining site) will be approached by the team to be included in the screening and treatment activity. They will be included in the analysis as a unit within a cluster of villages if all the study information can be collected (including follow-up survey for Group 1).

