6.4. Follow-up at 12 months (group 1 only)

6.4.1. Inclusion criteria

Randomly sampled individuals living in the village.

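### Group 1 villages and work settlements that received MSAT can be dropped from the primary incidence analysis on population change or survey availability at month 12, although malaria post data continue

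*Combined protocol and SAP*

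**What the plan says.** Section 7.8 lists two grounds under "An eligible village will be excluded from the study if". The first, that MSAT could not be carried out, is settled before treatment and is not at issue. The second is that "the population size changes by $\geq 50\%$ between MSAT and follow-up survey". Its stated scope is the study, not one outcome.

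Section 6.3.1 sets a similar condition for large work-related settlements (military, logging, mining): they are analysed within a cluster "if all the study information can be collected (including follow-up survey for Group 1".

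The population change becomes known through section 7.6.3: "Twelve months after the beginning of the MSAT campaign in group 1 villages (high incidence), a population list will be collected again". Section 6.4 and Appendix B also confine the 12-month survey and second demographic collection to group 1. The synopsis assigns the primary objective to groups 1 and 2.

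Primary data come from another source. Under 7.6.2 the malaria post reports weekly, 9.3 analyses 12 months of weekly data on each side of MSAT, and 7.9 keeps the posts running. Section 6.2 says that "the population of study villages will be included and monitored as a whole for the primary outcome on falciparum malaria incidence in the village". The denominator in 9.1 is the population measured at MSAT multiplied by the weeks with a report.

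**The concern.** A village's place in the analysis should be settled by the time it is treated. Here it depends on what happens to its population in the following year. Large influx or departure can plausibly affect reintroduction of infection and how long an MSAT effect lasts, so villages failing the rule may respond differently from those that pass. Removing them changes the question from the effect in treated villages to the effect in treated villages that turned out stable. In a non-randomised before/after comparison, no concurrent randomised arm offsets that selection.

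The incidence series of an excluded village exists and is complete enough to analyse. No section retains it, plans a sensitivity analysis, or gives a version of the 50% rule for group 2. A joint primary estimate would therefore combine group 1 villages filtered for stability with group 2 clusters that were not.

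**Working it through.** **1. Timing and data dependence.** The 50% rule needs the population at MSAT and at month 12, and so cannot be applied until about a year after treatment. The settlement condition in group 1 needs the month-12 survey. The primary model (9.3) needs weekly post counts and a population term. It does not need the survey. As written, both rules remove units from an analysis whose outcome data do not depend on the trigger.

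**2. Does the rule protect the denominator?** Section 9.3 names no population offset, so I assume the fixed MSAT population of 9.1 carries over. With an unchanged per-person rate, the apparent rate ratio is multiplied by (mean population in the year after MSAT) / (population at MSAT):

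| Change by month 12 | Step right after MSAT | Linear over the year |
|---|---|---|
| -50% | 0.50 | 1 - 0.50/2 = 0.75 |
| -49% | 0.51 | 1 - 0.49/2 = 0.755 |
| -30% | 0.70 | 0.85 |
| +30% | 1.30 | 1.15 |
| +50% | 1.50 | 1.25 |

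The problem is real, but the rule treats it as absent at 49% and disqualifying at 50%.

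**3. What interpolation achieves.** With person-time interpolated linearly between the two lists, a linear change is corrected in full (0.75/0.75 = 1; 1.25/1.25 = 1). A 50% step right after MSAT is corrected in part: 0.50/0.75 = 0.67 instead of 0.50, and 1.50/1.25 = 1.20 instead of 1.50.

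**4. Illustrative selection effect.** The documents give no frequency of changes of 50% or more and no effect in such villages. Assumptions: a share f of 5-15% of the 60 group 1 villages (3 to 9) is dropped, their rate ratio is 1.0, the ratio elsewhere is 0.5, and villages have equal weight. On the log scale, the all-treated ratio = 0.5^(1-f) x 1.0^f.
- f = 0.05: 0.5^0.95 = 0.52.
- f = 0.15: 0.5^0.85 = 0.55.

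The filtered analysis reports 0.50. If the dropped villages instead had a ratio of 0.25 (also an assumption), the all-treated value would be 0.5^1.05 = 0.48 to 0.5^1.15 = 0.45. The direction is therefore not determined.

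**5. Data lost.** With about 104 weeks per village: 3 x 104 = 312 to 9 x 104 = 936 village-weeks, half of them after MSAT.

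**6. Power.** The plan's prevalence figure reproduces. For 16% against 8%, two-sided alpha 0.05 (sidedness not stated) and power 0.80, n = 258 per period. The design effect is 1 + 59 x 0.15 = 9.85, and 258 x 9.85/60 = 42.4, rounded up to the stated 43 clusters. Power for this comparison is 0.92 with 60 villages and 0.90, 0.89 and 0.87 with 57, 54 and 51.

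For the primary outcome I used a Hussey-Hughes stepped-wedge variance with 6 steps of 10 villages, p = 0.25 per period, ICC 0.12, alpha 0.01 two-sided and power 0.90 (the plan's beta of 0.9 read as power). The standard error is 0.00509 with 190 inhabitants per village. The detectable difference is (2.576 + 1.282) x 0.00509 = 0.0196, or 19.6/1000, and 21.9/1000 after allowing for the 0.49 coefficient of variation in size. With 54 villages it is 20.7 to 23.1/1000. Both ranges stay below the stated 25/1000 on this per-period reading.

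**The case against.** The best defence is the fixed denominator. A village that halves or grows by half has an invalid population term, and keeping it uncorrected could distort its ratio by the factors in the table. This stands as a reason not simply to delete the rule: retention must come with updated person-time. It does not justify exclusion, because both group 1 population lists are already planned. The documents also do not state this motive.

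It can further be said that the 50% rule names a group 1 survey and so is a group 1 rule. That is a fair reading, but it confirms that the two groups are handled differently under one primary objective.

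Five stronger readings are tempting, and the documents do not support them:
- A reader might infer that villages are removed according to infection results at month 12. The triggers are population size and whether information was obtained.
- A reader might infer that neither rule can operate in group 2. The settlement condition expressly ties its survey requirement to group 1, so that inference holds only for the 50% rule.
- A reader might infer that a dropped camp's cases remain in the cluster's count, because 7.6.2 mentions "number of clinical malaria episodes treated by sex and age-group of patient and by parasite species" and not residence. That list is introduced as part of a wider report, and 10.2 lists individual clinical case data among the study records. Whether a camp's cases can be separated is not stated. Any false reduction from a camp that departs comes from the fixed denominator and would arise even if the camp were formally included.
- A reader might infer that the rule causes the two groups to be unlike. They differ by design (section 5). The rule adds a further difference in selection.
- A reader might infer that the bias must favour MSAT. Excluded villages could have done better or worse than the rest.

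**Conclusion.** The concern holds in this form. Sections 7.8 and 6.3.1 select treated units for the primary analysis on post-intervention events, although the incidence data do not depend on those events, and the 50% rule has no group 2 counterpart. As protection for the denominator, the rule leaves changes below 50% and all of group 2 uncorrected.

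The size and direction of the bias cannot be derived from the documents. The illustration of 0.52-0.55 against 0.50 applies to group 1 only and rests on assumed values for the share dropped, their rate ratio and equal weighting. Power is barely affected. The harm is to validity and interpretation, and is probably modest if few villages are excluded. The change is worth making because the data it needs for group 1 villages are already planned.

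**What to change.** - In 7.8, 6.3.1 and 9.3, state that every village that received MSAT stays in the primary incidence analysis, whatever its population or survey status at month 12.
- In group 1, replace the fixed denominator of 9.1 with person-time interpolated between the MSAT and month-12 population lists, and name this as the offset in 9.3. Count settlements for the weeks they were present where dates are known.
- Limit the 50% rule and the survey condition to the prevalence outcome.
- As a group 1 sensitivity analysis, repeat the primary analysis without villages that changed by 50% or more, and report how many there were.
- State that group 2 keeps the MSAT population, and that no equivalent check is possible there without a recount.

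The cost is wording in four sections, presence dates for settlements where obtainable, and one extra analysis. The downside is that some noisier clusters are kept, so the interval may widen slightly. Interpolated denominators are also approximate: an abrupt change is only partly corrected, and the year before MSAT still uses the MSAT population.
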